8.12 Discontinuation of Follow-Up

At any time during the study, the subject may withdraw their participation from the study. Follow-up is only discontinued at the explicit request of the patient. This decision should be an independent decision that is documented in the patient study files. Survival status should be collected within legal and ethical boundaries for all subjects randomized who withdrew participation from the study. Data generated from any patient withdrawn from the trial will be included in the analysis unless the patient explicitly forbids the use of any data which should be documented by the patient.

All patients are encouraged to return for all scheduled follow-up visits, and to provide appropriate contact information to accommodate completion of required telephone follow-ups. The investigator will attempt to contact the patient at each follow-up visit, independent of any missed follow-ups. The investigator should make 3 documented attempts per required follow-up visit.

Patients who have discontinued the trial prematurely will not be replaced.

8.13 Subjects Lost to Follow-Up

A subject would be considered lost to follow-up if he or she repeatedly fails to return for scheduled visits and is unable to be contacted by the study site. Site personnel are expected to make diligent attempts to contact subjects who fail to return for a scheduled visit. Survival status will be collected within legal and ethical boundaries for all subjects randomized. Vital status will be searched in public sources at the end of the 5 year follow-up period. If vital status is known, the subject will not be considered lost to follow-up.

9 STATISTICAL DESIGN AND ANALYSIS

9.1 Analysis Population(s)

9.1.1 Intent to Treat Population (ITT)

All clinical data in the ITT population will be analyzed according to randomized treatment. The ITT population set will consist of all patients who signed the written informed consent and are randomized, regardless if, and if so, which study stent was implanted.

9.1.2 Per Protocol (PP)

If required, an additional analysis of the Per-Protocol (PP) population will be conducted of the primary and secondary endpoints. The PP population consists of those patients who correctly received (only) the assigned study stent. If all patients correctly receive the assigned study stent(s), this analysis will not be required. If the patient has more than one lesion, for all lesions the assigned study stent must be used. If for a patient more than one lesion will be analyzed, no in-patient correlation will be taken into account.

9.2 Primary Analysis

The primary analysis is an ITT analysis of the primary endpoint, being TLF at 12-months. The study is powered at 85% to show non-inferiority for the MISTENT when compared to XIENCE. The analysis will also be conducted on the PP patient population, as required.

The primary endpoint of TLF will be analyzed and compared between the two treatment arms for non-inferiority of the MISTENT as compared to the control stent, XIENCE. The MISTENT expected TLF assumption is based on the assumption of no difference in event rates between MISTENT and XIENCE.

The 90% two-sided confidence interval for the difference in 12 months rates of TLF between the MISTENT and XIENCE arms will be calculated using Kaplan Meier estimates at 1 year and their standard deviations. If this 90% interval excludes the non-inferiority margin, MISTENT will be considered to be non-inferior to XIENCE (this accounts to one-sided non-inferiority testing at alpha = 5%).

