8.3 Baseline evaluation

All patients will have the following activities conducted prior to the PCI procedure:

- Baseline demographics and physical exam with pregnancy test (as required)
- Relevant medical and cardiac history
- Required anti-platelet medication(s)
- 12-lead electrocardiogram (within 72 hours)
- Cardiac biomarkers per standard of care and local practice is drawn prior to the index PCI procedure (within 24 hours prior to PCI). However it is preferred (if possible) to capture all 3 biomarkers: CK, CKMB and Troponin (I or T).
- Creatinine measurement (within 28 days prior to PCI)

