9.3 Sample Size Calculations

Primary Analysis:

The study is powered at 85% to show non-inferiority for the MISTENT when compared to XIENCE. The primary analysis will be based on an intent-to-treat (ITT) patient population, that is, all patients who are randomized to the specific study stent. Randomization should occur only after all inclusion/exclusion criteria, including angiographic evaluation, have been met. A

secondary evaluation will be conducted on patients that received only the assigned study stent at the target lesion(s).

Study Sample Size Calculation: 1400 Subjects

Assumptions:

- A 1:1 treatment allocation ratio of MISTENT to XIENCE
- a one-sided significance level (alpha) of 0.05
- 85% power to show non-inferiority of MISTENT to XIENCE
- a non-inferiority margin of 4%
- TLF event rate for XIENCE of 8.3% at 12M⁵
- TLF event rate for MISTENT of 8.3% at 12M
- maximum attrition rate of approximately 2%.

The 8.3% TLF rate is based on the XIENCE arm of the Resolute All Comers trial, the assumption is made that in DESSOLVE III the MISTENT arm will have the same event rate as the XIENCE arm. Using PASS software, and a standard normal distribution (Z-test) above assumptions require 682 subjects in the MISTENT arm and 682 in the XIENCE arm, for a total of 1364 patients, when not taking attrition into account. Accounting for loss to follow-up of approximately 2%, these numbers are increased to 700 and 700 respectively, for a total randomized sample of 1400 patients.

Primary Hypothesis and Statistical Analysis:

The primary endpoint of TLF will be analyzed and compared between the two treatment arms for non-inferiority of the MISTENT as compared to the control stent, XIENCE.

Secondary Endpoint Analysis:

Secondary endpoint analysis will occur at each follow-up visit and compared between the MISTENT and XIENCE groups.

For all clinical endpoints, the Kaplan-Meier method will be used.

For all secondary endpoints conventional p-values and 95% confidence intervals for the difference in Kaplan-Meier will be calculated.

Dichotomous variables will be evaluated using Fisher's exact tests. Continuous variables will be evaluated by a two-sample t-test.

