9.4 Subgroup Analysis

For these pre-specified subgroups, the MISTENT arm and XIENCE arm will be compared on an ITT basis:

- Diabetes
- STEMI
- Renal insufficiency (serum creatinine > 2.5mg/dL, or creatinine clearance \leq 30 mL/min)
- Small vessels (\leq 2.75mm)
- Multivessel treatment
- Long lesions ($>$ 18 mm)
- In-Stent restenosis
- Bypass graft
- Left Main treatment
- Bifurcation treatment
- Overlapping stents

For these subgroups, the primary endpoint and secondary endpoints will be evaluated. For these subgroups the study does not have significant power to demonstrate non-inferiority for the MISTENT arm to the XIENCE arm, meaning the results are considered exploratory (hypothesis-generating) only.

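### The primary 12-month TLF interval is valid but uses none of the prognostic data collected before PCI, so a small, low-cost gain in precision is left unused

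*Combined protocol and SAP*

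**What the plan says.** Section 9.2 tests non-inferiority with "The 90% two-sided confidence interval for the difference in 12 months rates of TLF between the MISTENT and XIENCE arms", which "will be calculated using Kaplan Meier estimates at 1 year and their standard deviations". No covariate or stratum enters. The design inputs in section 9.3 are "a one-sided significance level (alpha) of 0.05", "85% power to show non-inferiority of MISTENT to XIENCE", "a non-inferiority margin of 4" percentage points and "TLF event rate for XIENCE of 8.3% at 12M", with the same rate assumed for MISTENT. They lead to 682 per arm by a Z-test, raised to 700 for about 2% attrition.

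Section 8.3 lists what is done in every patient before PCI: demographics, "Relevant medical and cardiac history", an ECG, biomarkers and creatinine. Appendix I adds risk factors. Section 8.4 randomises in blocks within centre, once angiography has confirmed eligibility, and names no prognostic stratification factor.

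Section 9.4 names diabetes, STEMI and renal insufficiency among its subgroups and says only this of their analysis: "For these pre-specified subgroups, the MISTENT arm and XIENCE arm will be compared on an ITT basis". The Cox model at the end of section 9.3 names no covariates. Section 9 contains no adjusted analysis of the primary endpoint, either primary or supportive.

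**The concern.** This is an all-comers population, with stable and acute presentations in one trial, so baseline risk varies between patients. Part of the sampling error in a raw difference of two rates comes from chance differences in that risk between the arms. A standardised estimate removes the part that measured covariates explain and leaves the target, an absolute 12-month risk difference, unchanged.

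The data are already planned for collection, so the price is analytical work and no extra patient burden. There is also a practical risk. If a visible imbalance in diabetes or acute presentation appears, the plan has no pre-specified adjusted result to report, and one devised after the data are seen would be open to challenge whichever way it pointed.

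**Working it through.** **Inputs from section 9.3.** TLF 8.3% in both arms, margin 4 points, one-sided alpha 5% (z = 1.645), 85% power (z = 1.036), about 2% attrition.

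**Reproducing the plan's figure.** n per arm = 2 × 0.083 × 0.917 × (1.645 + 1.036)² / 0.04² = 684, against the stated 682. Power at 682 is 84.9%. The plan's number reproduces, and by an unadjusted method like that of section 9.2.

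**Baseline precision at 686 per arm** (700 × 0.98):
- SE = √(2 × 0.083 × 0.917 / 686) = 1.49 points
- 90% half-width = 1.645 × 1.49 = 2.45 points
- largest observed excess that still succeeds = 4 − 2.45 = 1.55 points
- power = Φ(4/1.49 − 1.645) = 85.1%

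**Effect of adjustment.** If baseline covariates explain a share R² of outcome variance, SE becomes SE × √(1 − R²). The documents give no R², so it has to be assumed. I took odds ratios of 1.6 for diabetes, 1.3 for STEMI, 2.5 for renal insufficiency and 1.35 per SD of age, with log odds ratios scaled by 0.6 to 1.4. Assumed prevalences were diabetes 25%, STEMI 20% and renal insufficiency 3%. R² is the variance of predicted risk divided by 0.083 × 0.917.

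| Assumed R² | SE (points) | 90% half-width (points) | Power at 686 per arm |
|---|---|---|---|
| 0 | 1.490 | 2.45 | 85.1% |
| 0.5% (scale 0.6) | 1.486 | 2.44 | about 85.2% |
| 3.3% (scale 1.4) | 1.465 | 2.41 | 86.1% |

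In patients, R² × 1372 gives a saving of about 7 to 45 in total. Adding multivessel disease (odds ratio 1.6, prevalence 40%) raises the top R² only to about 4.2%.

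**Does adjustment disturb the error rate?** Logistic standardisation with five covariates was simulated at 682 per arm, with 5,000 runs per setting and no censoring. Type I error at the 4-point margin was 5.1% to 5.8% adjusted and 5.1% to 5.6% unadjusted (Monte Carlo SE about 0.3 points). The variance ratio was 0.98 for a risk score with AUC about 0.64, which agrees with 1 − R² at R² = 2%.

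**Size of a chance imbalance.** Take one factor with assumed prevalence 25% and risk ratio 2. Risk is 0.083 / (0.75 + 0.25 × 2) = 6.64% without the factor and 13.28% with it. The 95% limit of imbalance at 700 per arm is 1.96 × √(2 × 0.25 × 0.75 / 700) = 4.54 percentage points, which shifts the difference by 0.0454 × 6.64 = 0.30 points. Over prevalences of 20% to 35% and risk ratios of 1.5 to 2.5 the shift is about 0.2 to 0.4 points. For the adjusted factors together, the SD of the shift is 1.49 × √R² = 0.11 to 0.27 points.

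**The case against.** The strongest reply is that nothing is broken. A raw Kaplan-Meier difference is unbiased under randomisation, its interval already allows for chance imbalance, it agrees with the sample-size method, and planned power is met without adjustment. All of that stands. It makes this a suggestion about efficiency and not a correction of an error.

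Four further points stand and limit the claim:

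- **Timing of the data.** A reader might infer that the prognostic factors are recorded before randomisation. Section 8.3 says before PCI, and under section 8.4 the implant follows allocation. Age and established diabetes pre-exist in any case, but operators are unblinded (section 8.5.1), so the values used should be those established before allocation.
- **Choice of factors.** Many section 9.4 subgroups describe the lesion or the procedure, such as overlapping stents or multivessel treatment. They do not support baseline adjustment, and some may follow allocation. The renal subgroup definition is strict (creatinine above 2.5 mg/dL or clearance of 30 mL/min or less) and may apply to few patients.
- **Cost.** The change needs an outcome model, a way to handle censoring and a rule for missing covariates. It is cheap but not free.
- **Timing of the change.** The table of changes for version 2.0 (dated 07 March 2018) gives early results suggesting a benefit of MiStent as the reason for longer follow-up. The documents do not say which results these are. If comparative 12-month data had been seen, replacing the primary estimator would itself look data-driven.

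A reader might also set the 1.55-point threshold beside chance imbalance and infer that imbalance could easily decide the trial. The calculation does not support this: a single-factor imbalance at its 95% limit moves the difference by about 0.2 to 0.4 points, and the interval already allows for it.

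**Conclusion.** The point holds as a small, low-cost improvement. The interval in section 9.2 is valid and consistent with section 9.3, but it leaves unused the prognostic data already collected, and no adjusted estimate of the primary endpoint is pre-specified. For age, diabetes, acute presentation and renal function, the expected gain is 0.01 to 0.04 points of half-width and roughly 0.1 to 1.0 points of power.

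These sizes rest on odds ratios and prevalences that are not in the documents, and on the approximation that variance falls by the factor 1 − R². They model STEMI for acute presentation and a binary renal factor, so the broader acute-presentation category and continuous renal function could give somewhat different figures. The documents do not support reading this as bias, an invalid test or a shortfall in power.

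**What to change.** Add to the SAP one covariate-standardised 12-month TLF risk difference:

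- **Estimator:** g-computation with pseudo-values or censoring weights, a robust or bootstrap 90% interval, and the same 4.0-point margin. A covariate-adjusted hazard or odds ratio will not serve, because the margin is an absolute difference.
- **Covariates:** age, diabetes, acute presentation and renal function (creatinine or clearance, preferably continuous). Use values established before allocation and no procedural factors. State the functional form and a rule for missing covariates.
- **Role:** primary only if fixed before any comparative 12-month data are seen. Otherwise report it as supportive and labelled with its timing. In either case show the raw Kaplan-Meier interval beside it.

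The cost is SAP text, modest programming and a less familiar estimator to explain. Sample size, margin and data collection do not change.

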9.3 Sample Size Calculations

Primary Analysis:

The study is powered at 85% to show non-inferiority for the MISTENT when compared to XIENCE. The primary analysis will be based on an intent-to-treat (ITT) patient population, that is, all patients who are randomized to the specific study stent. Randomization should occur only after all inclusion/exclusion criteria, including angiographic evaluation, have been met. A

secondary evaluation will be conducted on patients that received only the assigned study stent at the target lesion(s).

Study Sample Size Calculation: 1400 Subjects

Assumptions:

- A 1:1 treatment allocation ratio of MISTENT to XIENCE
- a one-sided significance level (alpha) of 0.05
- 85% power to show non-inferiority of MISTENT to XIENCE
- a non-inferiority margin of 4%
- TLF event rate for XIENCE of 8.3% at 12M⁵
- TLF event rate for MISTENT of 8.3% at 12M
- maximum attrition rate of approximately 2%.

The 8.3% TLF rate is based on the XIENCE arm of the Resolute All Comers trial, the assumption is made that in DESSOLVE III the MISTENT arm will have the same event rate as the XIENCE arm. Using PASS software, and a standard normal distribution (Z-test) above assumptions require 682 subjects in the MISTENT arm and 682 in the XIENCE arm, for a total of 1364 patients, when not taking attrition into account. Accounting for loss to follow-up of approximately 2%, these numbers are increased to 700 and 700 respectively, for a total randomized sample of 1400 patients.

Primary Hypothesis and Statistical Analysis:

The primary endpoint of TLF will be analyzed and compared between the two treatment arms for non-inferiority of the MISTENT as compared to the control stent, XIENCE.

Secondary Endpoint Analysis:

Secondary endpoint analysis will occur at each follow-up visit and compared between the MISTENT and XIENCE groups.

For all clinical endpoints, the Kaplan-Meier method will be used.

For all secondary endpoints conventional p-values and 95% confidence intervals for the difference in Kaplan-Meier will be calculated.

Dichotomous variables will be evaluated using Fisher's exact tests. Continuous variables will be evaluated by a two-sample t-test.

⁵ Serruys PW, Silber S, Garg S, van Geuns RJ, Richardt G, Buszman PE, Kelbaek H, van Boven AJ, Hofma SH, Linke A, Klauss V, Wijns W, Macaya C, Garot P, DiMario C, Manoharan G, Kornowski R, Ischinger T, Bartorelli A, Ronden J, Bressers M, Gobbens P, Negoita M, van Leeuwen F, Windecker S. Comparison of Zotarolimus-Eluting and Everolimus-Eluting Coronary Stents. NEJM 2010;363:136-46.

For time-dependent analyses, Hazard Ratios will be evaluated using Cox proportional hazards model and Kaplan Meier estimates will be evaluated according to log-rank test.

9.4 Subgroup Analysis

For these pre-specified subgroups, the MISTENT arm and XIENCE arm will be compared on an ITT basis:

- Diabetes
- STEMI
- Renal insufficiency (serum creatinine > 2.5mg/dL, or creatinine clearance \leq 30 mL/min)
- Small vessels (\leq 2.75mm)
- Multivessel treatment
- Long lesions ($>$ 18 mm)
- In-Stent restenosis
- Bypass graft
- Left Main treatment
- Bifurcation treatment
- Overlapping stents

For these subgroups, the primary endpoint and secondary endpoints will be evaluated. For these subgroups the study does not have significant power to demonstrate non-inferiority for the MISTENT arm to the XIENCE arm, meaning the results are considered exploratory (hypothesis-generating) only.

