2.7 Study Objectives

This protocol will provide data to comply with regulatory requirements as well as gain substantial additional information on patients in a real world setting. This protocol will compare clinical outcomes of the MISTENT and XIENCE in a broad patient and lesion population. These data may also be used to support regulatory approvals in other countries and provide data on various lesion types that may be treated in order to expand the indications for MISTENT.

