8.6 Stent implant Procedure

Please follow each manufacturer's respective Instructions for Use provided with the device. The investigator will choose the appropriate length and diameter of the stents to be implanted by visual estimate. The choice of the length of the stent should ensure complete coverage of the entire lesion. If multiple stents are required, the distal stent should be placed first and the second stent should be overlapping so that there are no gaps between stents with at least 5 mm overlap of stents. In case of insufficient stent expansion, the stent will be post-dilated with an appropriately sized balloon.

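### Section 9.4 compares the arms within subgroups without an interaction analysis, and the overlapping-stents class is formed after randomisation

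*Combined protocol and SAP*

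**What the plan says.** Section 9.4 (Subgroup Analysis) names 11 classes: diabetes, STEMI, renal insufficiency, small vessels, multivessel treatment, long lesions, in-stent restenosis, bypass graft, left main treatment, bifurcation treatment and, last, "Overlapping stents". The method is one sentence: "For these pre-specified subgroups, the MISTENT arm and XIENCE arm will be compared on an ITT basis". The primary and secondary endpoints are both to be evaluated. The section adds that power in these classes is insufficient for non-inferiority and that the results are exploratory only. Neither an interaction analysis nor multiplicity is mentioned.

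The order of events comes from other sections:

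- Section 8.4: patients are randomised once the baseline angiogram has confirmed eligibility.
- Section 8.6: the investigator then chooses stent length and diameter by eye, and "If multiple stents are required, the distal stent should be placed first and the second stent should be overlapping".
- Section 8.5.1: the implanting investigator is not blinded.
- Section 8.7: staged procedures, in a different epicardial vessel, may follow up to 45 days later. Section 9.6 counts event time from the index procedure.

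On use of the data, section 2.7 says they may support regulatory approvals elsewhere and "provide data on various lesion types that may be treated in order to expand the indications for MISTENT".

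**The concern.** There are two separate problems.

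First, the question a subgroup analysis should answer is whether the device effect differs between classes. A set of within-class comparisons does not answer it. One class may look positive and another not because of size or chance alone, or because a uniform effect happens to show in the larger classes.

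Second, whether stents overlap is decided after allocation, by someone who knows the allocation, and may depend on how the assigned stent behaved (an uncovered lesion end, an edge problem, a bail-out). Randomisation balances the arms at allocation. It does not balance the patients who later enter a class that the allocation can influence. Keeping each patient in the assigned arm, which is what ITT secures, does not repair that. Two equivalent devices could therefore appear to differ within the overlap class.

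At stake is how the lesion-type results are read, not the primary conclusion.

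**Working it through.** **The plan's own figure.** Section 9.4 gives no number to reproduce. The primary sample size in section 9.3 serves as the check on inputs: "a one-sided significance level (alpha) of 0.05", "85% power to show non-inferiority of MISTENT to XIENCE", "a non-inferiority margin of 4" percentage points, "TLF event rate for XIENCE of 8.3% at 12M", and the same rate assumed for MISTENT.

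n per arm = 2 x 0.083 x 0.917 x (1.645 + 1.036)^2 / 0.04^2 = 684, against 682 stated. Power at 682 per arm is 84.9%. The plan's figure is reproduced to within two patients.

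**Power within a class.** The documents give no class sizes, so the shares below are assumptions. With n_s = share x 700 per arm, power = Phi(0.04 / sqrt(2 x 0.083 x 0.917 / n_s) - 1.645), where Phi is the standard normal distribution function.

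| Share of patients | n per arm | Non-inferiority power | 90% half-width |
|---|---|---|---|
| 5% | 35 | 15% | 10.9 points |
| 10% | 70 | 22% | 7.7 points |
| 20% | 140 | 33% | 5.4 points |
| 30% | 210 | 44% | 4.4 points |
| 50% | 350 | 61% | 3.4 points |

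This confirms what section 9.4 already concedes, and is not itself a defect.

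**Chance findings.** If each class were tested two-sided at 5% on one endpoint, with no true difference:

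- 11 independent tests: 1 - 0.95^11 = 43.1%.
- 2,000 simulated trials of 1,400 patients, 8.3% TLF in both arms, assumed class shares of 3 to 40%: at least one p < 0.05 in 39.9% with uncorrelated classes and 35.3% with a latent correlation of 0.3.

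The range is therefore about 35 to 43% for one endpoint at one time point.

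**What each analysis detects.** The same simulation (correlation 0.3) with MISTENT better by 3 points in every patient, so with no heterogeneity at all:

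- Within-class tests flag at least one class in about 65% of trials.
- Unadjusted interaction tests flag at least one in about 41%, much as under no difference (40 to 41%).
- Interaction tests at 0.05/11 = 0.0045 flag at least one in about 4%.

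So within-class results respond to the overall effect. Interaction estimates address heterogeneity, but testing them at 5% does not reduce chance findings.

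**Post-allocation membership.** The documents give no overlap rate and no TLF rate by overlap, so this is illustrative only. Suppose 15% of each arm would overlap whichever device was assigned, with 12% TLF, and a further share s enters the class in one arm only, with TLF r. With equal devices:

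apparent difference = (0.15 x 0.12 + s x r) / (0.15 + s) - 0.12

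- s = 2%, r = 5%: (0.018 + 0.001) / 0.17 - 0.12 = -0.8 points
- s = 2%, r = 25%: (0.018 + 0.005) / 0.17 - 0.12 = +1.5 points
- s = 6%, r = 5%: (0.018 + 0.003) / 0.21 - 0.12 = -2.0 points
- s = 6%, r = 25%: (0.018 + 0.015) / 0.21 - 0.12 = +3.7 points

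Either sign is possible. In the last case (105 against 147 patients) the 90% half-width is 1.645 x sqrt(0.12 x 0.88/105 + 0.157 x 0.843/147) = 7.2 points, so the bias lies inside the sampling noise. The interval makes no allowance for it, however.

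**The case against.** The strongest reply is that section 9.4 already calls the results exploratory and underpowered, and that no confirmatory claim hangs on them. That stands, and it is why the point is minor. It does not dispose of the point: the label is argued from low power, and a biased comparison also makes a poor hypothesis.

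Four further replies have weight:

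- Section 9.4 speaks of comparing and evaluating and does not mention p-values. The p-value sentence in section 9.3 concerns secondary endpoints. That nominal within-class tests will be made is therefore an inference, and the 35 to 43% is conditional on it.
- The synopsis restricts XIENCE to comparable sizes up to 30 mm, and section 3.1 gives MISTENT lengths of 9 to 30 mm. This reduces any difference between arms in the need for overlap, though not differences arising from device behaviour or operator choice.
- An interaction test alone would not lower the chance of a spurious positive, as the working shows. The fix therefore needs a statement on multiplicity too.
- The summary of changes explains the extension of follow-up by early results. New data entry before randomisation may therefore come too late.

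A reader might also infer that testing both levels of each class gives 1 - 0.95^22 = 68%. The plan does not say the complementary levels will be tested, and they are far from independent of one another, since the complement of a rare class is nearly the whole trial. Simulation with both levels tested gave 44 to 47%.

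**Conclusion.** The point holds, as a minor one. As written, section 9.4 does not answer whether the device effect varies by class, and its overlapping-stents comparison is not protected by randomisation. The second statement rests on the sequence in sections 8.4, 8.5.1 and 8.6 and on the absence of any definition of overlap as planned at baseline. For multivessel, left main and bifurcation treatment the risk is conditional: they are named by treatment, and section 9.4 does not say when membership is fixed. If multivessel status counts staged procedures, it could be settled after event time has begun.

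The 35 to 43% assumes nominal 5% tests, equal devices and one endpoint; the simulated end also assumes class shares. The overlap bias has no size that the documents can supply.

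Two stronger readings are tempting. One is that the subgroup results are the route to wider indications. Section 2.7 says this of the trial's data generally and does not name section 9.4, so the link is an inference. The other is that false positive subgroup claims are to be expected from overlap. The documents show that the comparison is unprotected, but neither the direction nor the size of any distortion. The primary ITT analysis, the margin and the sample size are unaffected.

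**What to change.** In section 9.4:

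1. For each subgroup, report the treatment-by-subgroup interaction for 12-month TLF with its confidence interval, beside the within-subgroup estimates and intervals. Give no stand-alone within-subgroup p-values.
2. State that no multiplicity adjustment is made and that chance findings are expected across 11 classes.
3. Report overlapping stents descriptively only, or replace it with a class based on lesion length recorded at baseline, for example any lesion longer than 30 mm, the longest stent in either arm. The long-lesion class already in section 9.4 implies that lesion length is available; confirm that it is taken from the pre-procedure angiogram.
4. Define the multivessel, left main and bifurcation classes from baseline lesion features, not treatment delivered, using existing baseline data where enrolment is complete.
5. Add a sentence reconciling section 2.7 with the exploratory label.

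The cost is wording and a little more analysis, with no change to sample size or the primary test. The downside is that a lesion-length class answers the overlap question only by proxy.
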